## 1.0 Objectives

1.1 Primary: To assess the feasibility of blinatumomab post allogeneic hematopoietic cell transplantation (HCT) as consolidation therapy in patients with B-lineage acute lymphoblastic leukemia (ALL). Toxicities attributable to blinatumomab, acute GVHD, and secondary graft failure will be the parameters to define feasibility.

1.2 Secondary:

1.2.1 To evaluate the progression-free survival (PFS) rate at 1-year for patients with ALL compared to contemporary patient cohort.

1.2.2 To evaluate other efficacy endpoints such as overall survival (OS) and minimal residual disease (MRD) negativity rate in patients treated with blinatumomab for consolidation therapy.

1.2.3 To evaluate, non-relapse mortality (NRM) and chronic GVHD.

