### 4.2 Exclusion criteria:

1. Relapsed ALL defined as >5% malignant blasts in bone marrow or peripheral blood.
2. Active GVHD requiring systemic steroid therapy. Medications for GVHD prophylaxis are acceptable.
3. Systemic steroid therapy unless for physiologic replacement
4. Uncontrolled disease/infection as judged by the treating physician
5. Active ALL in the central nervous system (CNS), as defined by  $\geq 5$  leukocytes per  $\mu L$  with identifiable blast cells in the CSF (CNS 3 disease), and/or the presence of cranial-nerve palsies.
6. Pregnant or nursing women

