### **8.2 Primary Objectives**

The primary objective in this trial is feasibility. Treatment-related toxicities attributable to blinatumomab, an excess rate of acute GVHD, and an excess rate of secondary graft failures will be the parameters to determine feasibility. The successful completion of the trial without reaching stopping rules will indicate that the primary objective of the trial was met. Cumulative incidence time to GVHD will be computed from the date of allogeneic HCT to the date of event. The cumulative incidence (CI) of GVHD will be determined using the competing risks method. The competing risks included will be relapse and death, and patients who do not experience GVHD or relapse and are still alive at the last follow-up date will be censored at that date.

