#### 8.3.5 Continuous Toxicity Monitoring

Continuous monitoring of toxicity will be assessed for all treated patients, beginning with the first cohort of five patients. Assuming a prior beta distribution of (0.6, 1.4), the study will terminate if the  $\Pr(\delta_t > 0.30 | \text{data}) > 0.85$ , where  $\delta_t$  is the toxicity rate attributable to the treatment. Toxicities are defined as any 1) grade 3-4 acute GVHD greater than 30%, 2) secondary graft failure >30%, or 3) NRM within one cycle of blinatumomab (i.e., 30 days). The decision rule for terminating for toxicity is presented in Table 5 and the operating characteristics for this rule are presented in Table 6. The method used to produce the decision rule and operating characteristics was designed by Thall, Simon, and Estey (1995).

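### The feasibility verdict tests only grade 3-4 acute GVHD, while the objective names acute GVHD without a grade, and the one other GVHD estimate cannot fill the gap

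*Combined protocol and SAP*

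**What the plan says.** Four places in the combined protocol and SAP bear on this.

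- **Objective (1.1).** "Toxicities attributable to blinatumomab, acute GVHD, and secondary graft failure will be the parameters to define feasibility". No grade is attached to acute GVHD.
- **Primary analysis (8.2).** The parameters are restated as "an excess rate of acute GVHD, and an excess rate of secondary graft failures will be the parameters to determine feasibility", again with no grade and with no reference rate against which an excess would be judged. The verdict is then fixed by one criterion: "The successful completion of the trial without reaching stopping rules will indicate that the primary objective of the trial was met". The same section plans a competing-risks cumulative incidence of GVHD, timed from transplant, with relapse and death as competing events. It attaches no grade, limit or comparator to that estimate.
- **Stopping rule (8.3.5).** "Toxicities are defined as any 1) grade 3-4 acute GVHD greater than 30%, 2) secondary graft failure >30%, or 3) NRM within one cycle of" the study drug, that cycle being given as 30 days. This is the only place where acute GVHD receives a grade.
- **Entry (4.1 and 4.2).** Patients enrol 30 to 100 days after transplant. "Active GVHD requiring systemic steroid therapy" is an exclusion; GVHD that has resolved, or that is managed without systemic steroids, is not.

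**The concern.** The objective is wider than the test that decides it. A reader told that the primary objective was met will look back to 1.1 and conclude that acute GVHD was examined and found acceptable. In fact the verdict will have examined grade 3-4 acute GVHD, pooled with graft failure and early non-relapse mortality. Acute GVHD below grade 3 cannot change it.

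The planned cumulative incidence does not repair this. It has no grade split, so it cannot show what lies below grade 3. Because its clock starts at transplant, an episode in the weeks before the first dose counts the same as one that follows blinatumomab. What is at stake is the wording of the primary conclusion and whether the report can show how much acute GVHD arose on treatment.

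**Working it through.** **Inputs.** From 8.3.5: prior Beta(0.6, 1.4), toxicity limit 0.30, posterior cutoff 0.85, first look at 5 patients. From Table 5: boundaries for 5 to 29 patients, maximum 30. From Table 6: stated probabilities of stopping early. I read the counted event as a per-patient event (grade 3-4 acute GVHD, secondary graft failure, or early non-relapse mortality), which is the reading under which a single toxicity rate makes sense.

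**Step 1: reproduce Table 5.** With x counted events in n patients the posterior is Beta(0.6 + x, 1.4 + n − x). The boundary is the smallest x for which the posterior probability of a rate above 0.30 exceeds 0.85.

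- n = 5, x = 3: Beta(3.6, 3.4) gives 0.8745, stop. With x = 2: Beta(2.6, 4.4) gives 0.6261, continue.
- n = 29, x = 12: Beta(12.6, 18.4) gives 0.8897, stop. With x = 11: Beta(11.6, 19.4) gives 0.8008, continue.

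Every boundary from n = 5 to n = 29 agrees with Table 5.

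**Step 2: reproduce Table 6.** Exact binomial recursion, with a look after every patient from 5 to 29:

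| True rate of counted events | Recomputed Pr(stop early) | Table 6 |
|---|---|---|
| 0.10 | 0.010 | 0.01 |
| 0.20 | 0.097 | 0.10 |
| 0.30 | 0.358 | 0.36 |
| 0.40 | 0.718 | 0.72 |
| 0.50 | 0.938 | 0.94 |

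A hand check at 0.10: the first look alone stops with probability 10(0.1³)(0.9²) + 5(0.1⁴)(0.9) + 0.1⁵ = 0.0081 + 0.00045 + 0.00001 = 0.0086, most of the 0.010. The rule's arithmetic is sound.

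**Step 3: what the verdict depends on.** Let p be the probability that a patient has a counted event, and q the probability of acute GVHD that never reaches grade 3 in a patient with no counted event. After n patients the number of counted events is Binomial(n, p). The boundary uses only that number, so the probability of stopping is a function of p alone. At p = 0.10 the trial completes and is called feasible with probability 1 − 0.010 = 0.990 for every q. GVHD that starts mild and later reaches grade 3 is already in p.

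**Step 4: can the 8.2 cumulative incidence supply what is missing?** Set 8.2 beside 4.1 and 4.2. The clock starts at day 0 and enrolment is at day 30 to 100, so for each patient the first 30 to 100 days of the curve precede enrolment. An earlier episode that has resolved or does not need systemic steroids is compatible with entry, so pre-treatment GVHD can be in the curve. No statement in 8.2 separates it, grades it, or ties the estimate to the conclusion.

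**The case against.** The best reply is that this is ordinary drafting: a general objective in 1.1 is made operational in the statistics section, and counting only severe events in a stopping rule is a legitimate design choice. That stands, and it is why the boundary should not move. It does not settle the wording, because 8.2 gives the boundary the whole verdict while still describing the parameter without a grade.

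A second reply is that lower-grade GVHD is not ignored. Table 4 requires a GVHD assessment before each cycle and at completion, and 8.2 plans an incidence estimate. True, so the data can be reported. What is missing is the grade split, a start at first dose, and a stated place beside the verdict.

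Several stronger readings are tempting, and the documents do not support them.

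- **That the protocol promises to test GVHD of any grade.** It says nothing about grade in 1.1 or 8.2. Ungraded is the accurate word.
- **That 4.2 makes steroid-requiring GVHD a toxicity threshold, or a bar to later cycles.** It is an entry criterion, it says active GVHD rather than acute, and it has no grade limit. Neither the dose-modification section (3.3) nor the removal criteria (7.0) names GVHD.
- **That lower-grade GVHD is the commoner signal and would make four cycles impractical.** The documents give no rate by grade and no such consequence. Their background (2.1 and 2.5) points to low GVHD risk, though from patients treated after relapse.
- **That the 0.36 or 0.94 in Table 6 measures the harm.** Those figures would apply only if lower-grade GVHD were counted under the same boundary and brought the combined rate to 30% or 50%. The rule was not set for that composite, and I do not propose monitoring it. That an uncounted event leaves the stopping probability unchanged is true of any uncounted event.

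**Conclusion.** The point holds as a mismatch between claim and test, not as an error in the stopping rule. Completing the trial can support feasibility with respect to grade 3-4 acute GVHD, within the pooled toxicity rate. It cannot support feasibility with respect to acute GVHD as 1.1 and 8.2 word it, and the planned cumulative incidence cannot extend it, being ungraded and timed from transplant.

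The size of the gap is unknown, because the documents give no rate of acute GVHD below grade 3 and do not say which grades need systemic steroids. What can be stated is that the verdict is insensitive to it: at a counted-event rate of 10% (a row of Table 6, taken as an illustration) the probability of stopping early is 0.01 at any rate of lower-grade GVHD. The conclusion rests on reading 8.2 literally, that the stopping rule alone decides whether the objective is met. It is worth correcting because the correction is cheap and changes what the trial may claim.

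**What to change.** 1. Leave Tables 5 and 6 and the 8.3.5 boundary as they are.
2. In 1.1 and 8.2, state that completing the trial without reaching the stopping rule supports feasibility with respect to grade 3-4 acute GVHD only.
3. In 8.2, add a cumulative incidence of new acute GVHD timed from the first blinatumomab dose, reported by grade and by need for systemic steroids, with relapse and death as competing events and a confidence interval. Say what counts as new in a patient who enters with GVHD not needing systemic steroids, and exclude dexamethasone given under 3.2 and 3.3 from the steroid criterion.
4. Report that estimate beside the verdict, as description rather than as a second test.

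**Cost.** The claim becomes narrower. Section 9.1 already asks for onset date and maximum grade of adverse events, but 5.2 keeps concomitant medications out of the CRF. Steroid start dates and their indication would therefore have to be abstracted from the medical record for about 30 patients. The estimate will be imprecise: ignoring censoring, at an assumed incidence of 20% in 30 patients the standard error is √(0.2 × 0.8 / 30) = 0.073, so a 95% interval is roughly ±1.96 × 0.073 = ±0.14. Sample size, boundary and treatment rules do not change.

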## 2.0 Background

2.1 Risk for relapse following HCT

Allogeneic HCT is a curative approach for a select group of patients with ALL. Overall survival (OS) ranges from 30%-60%

depending on the patients disease stage and risk profile at time of transplant (1,2).

Increasingly, minimal residual

disease (MRD), both before and after HCT, is becoming an important predictor for relapse (3). In a series of 149 ALL patients transplanted in remission at MD Anderson Cancer Center, patients with MRD, measured by multiparameter flow cytometric immunophenotyping (FCI) with a sensitivity of 0.01%, present at time of HCT had a shorter PFS compared to patients who were MRD negative, 28% vs. 47%,  $p=.08$  (4). Furthermore, among 135 patients who had MRD measured following HCT, 20 became positive for MRD, and 18 of these patients developed

[figure not shown]
[figure not shown]

Figure 1. With a median follow-up of 13 months, 2-year DFS rates are 61%, 40% and 33% for patients in CR1, CR2, and more advanced disease respectively.

overt hematologic relapse within a median of 3.8 months (4). Of note, among 32 patients with overt relapse following HCT, 41% did NOT have preceding MRD, suggesting that positive MRD post HCT essentially confirms eventual relapse, but negative MRD post HCT in a high-risk patient does not preclude relapse. Our findings corroborate similar published studies (5,6). Patients transplanted beyond second remission routinely have a significantly lower PFS and OS rates. In our study of 97 patients (CR1 51, CR2 29, others 17) treated with busulfan and clofarabine chemotherapy conditioning following a matched sibling (MSD) or matched unrelated donor (MUD) transplant, patients in CR1 had a significantly better disease free survival (DFS) compared with others (Figure 1). For patients in CR1, the 2-yr DFS rate was 61% with 9/51 patients relapsing at median 9 months, the 2-yr DFS rate was 40% for CR2, with 10/29 relapsing at median 3 months, and for patients with more advanced disease, the 2-yr DFS rate was 33% with 3/17 progressing at a median of 3 months. Our preliminary results with this regimen were similar (7). Data from the Center for International Blood and Marrow Transplant Research (CIBMTR) corroborate our findings. Between 1996 and 2001, in patients less than 20 years-old, OS ranges from 25% for patients transplanted beyond first remission to 50% for sibling transplants in first remission. Similarly, in adult patients, greater than 20 years-old, the best outcome is noted in sibling transplants done in first remission with OS of 60%, as compared to 35% if transplants are performed beyond CR1 (CIBMTR Registry).

In pediatric patients with B cell precursor acute lymphoblastic leukemia, cure rates with chemotherapy (in combination with radiotherapy in certain situations) can be as high as 80-85%. Children with second or greater relapse or refractory disease have dismal prognosis even when treated with allogeneic stem cell transplantation which is usually reserved for patients with high-risk features (i.e. poor-risk cytogenetic markers), those who fail to achieve remission or relapse after standard or intensive chemotherapy. From the CIBMTR data base, among the 1,569 patients younger than 18 years receiving an HLA-matched sibling transplant for ALL between 2005 and 2015, the 3-year probabilities of survival were  $73\% \pm 2\%$ ,  $58\% \pm 2\%$ , and  $40\% \pm 5\%$  for patients with early (CR1), intermediate (second or subsequent CR), and advanced disease (primary induction failure and advanced disease), respectively. The corresponding probabilities of survival among the 2,845 recipients of an unrelated donor transplant were  $68\% \pm 2\%$ ,  $56\% \pm 1\%$ , and

## Survival after HLA-Matched Sibling Donor HCT for ALL, Age <18 Years, 2005-2015

43%  $\pm$  4%. Disease relapse represent the most common cause of death post-transplant.

No effective treatment options exist for patients who relapse following HCT. Multiple published series report less than 10% survival for these patients, regardless of the treatment modality used, with a median survival of 2-3 months (2,8). To date, the most common

strategy employed to reduce relapse rates after HCT has usually involved some form of immune manipulation, ranging from donor lymphocyte infusion (DLI) to second transplant (9-12). However, although it has been consistently shown that patients with B-ALL who develop graft-versus-host-disease (GVHD) have less risk for relapse (13), DLI has not shown appreciable efficacy in this patient population; remission rates have been less than 10%, and have been associated with a high incidence of GVHD (14). Of note, the best responses to DLI in ALL occur when the DLI is administered prophylactically to prevent relapse (10); this approach has been demonstrated in pediatric patients but no data for prophylactic DLI has been reported in adults.

Thus, there is an unmet need for effective therapy for ALL patients at high risk for relapse following allogeneic HCT, with high risk defined as positive MRD and/or disease beyond first complete remission. Blinatumomab has demonstrated efficacy in both the MRD setting (15, 16) and for patients with active disease (17). Importantly, since its mechanism of action is through immune modulation rather than cytotoxicity, it has a favorable risk profile with minimal cytopenias noted in patients (18). Furthermore, a recent series of 9 pediatric patients (19) and our personal experience in patients treated with blinatumomab after relapse following HCT indicate a low risk for GVHD.

### 2.2 Blinatumomab

The Bispecific T-cell Engaging (BiTE) antibody blinatumomab represents the first agent in a class that redirects host T-cells to cell surface antigen-expressing cancer cells. Blinatumomab contains the variable domains of a CD19 antibody and a CD3 antibody which are joined by a non-immunogenic linker (20). Upon binding to CD19, the cytotoxic T cells become activated and induce cell death via the pore-forming perforin system. The drug was initially administered as an intermittent infusion two to three times weekly, but lack of activity and serious neurologic

toxicity caused the schedule of administration to be abandoned (20). Based on the short half-life of the drug and the mechanism of action, continuous infusion over several weeks were investigated. This drastically improved the activity of the drug, particularly in ALL, and helped reduce adverse effects.

### 2.3 Blinatumomab and MRD

The first study with blinatumomab used as continuous infusion evaluated its potential role in eradicating MRD (15). MRD-positivity in ALL almost universally heralds systemic relapse and confers poor prognosis. Patients treated in this study were in hematologic and morphologic CR, but had persistent or reappearing MRD during consolidation chemotherapy. Blinatumomab was given at a dose of 15  $\mu\text{g}/\text{m}^2/\text{day}$  as a continuous infusion for 28 days every 6 weeks (14 days off) (15). After completing one cycle, responding patients could receive up to three additional consolidation cycles or proceed to ASCT if a donor is available. MRD conversion after one cycle was observed in 16 of 20 evaluable patients (80%). In a long-term follow up update (median observation time 33 months), 12 of the 20 patients remained in CR. The estimated 3-year relapse-free survival was 60% (16). Nine patients underwent ASCT, but interestingly, non-transplanted patients had similar favorable outcome compared to the transplant group. Most relapses after blinatumomab treatment occurred early, within seven months of the start of therapy. In a confirmatory open-label multicenter phase II trial in 116 patients in morphologic CR with positive MRD positive, the overall rate of conversion to the MRD negativity was 80% (78% occurring after one cycle of treatment) (21).

### 2.4 Blinatumomab in relapsed and refractory ALL

Blinatumomab was subsequently studied in patients with active systemic ALL relapse. In a confirmatory open-label, single-arm, multicenter phase II study in 189 patients with relapsed-refractory disease, blinatumomab was administered as the overall response rate was 43% with 80% of the responses occurring within cycle 1. The median response duration and overall survival were 9 and 6 months, respectively (Table 1) (17).

In a pediatric phase I/phase II study of blinatumomab in relapsed/refractory ALL (defined as second or later bone marrow relapse, any marrow relapse after ASCT, or refractory to other treatments, and had > 25% blasts in bone marrow), among the 70 patients (median age 8 years, range 7 months to 17 years) who received the recommended dosage (15  $\mu\text{g}/\text{m}^2/\text{day}$  for 28 days and 2 weeks treatment free per cycle), 27 (39%) achieved CR within the first two cycles, 14 (52%) of whom achieved complete minimal residual disease response. 40 out of 70 (57.1%) had undergone allogeneic HSCT prior to receiving blinatumomab, and 39 out of 70 (55.7%) had refractory disease. The median number of treatment cycles was 1 (range 1 to 5) (23).

## 2.5 Blinatumomab toxicity profile

The toxicity profile of blinatumomab has been largely consistent with historical studies, with fever, chills, and hypogammaglobulinemia occurring frequently. Tremor, headache, and other mental status changes (e.g., confusion) have been reported. Fever, chills, and other constitutional symptoms are thought to be due to a cytokine release syndrome that occurs shortly after the start of therapy and are reduced with the use of steroids (e.g. dexamethasone 8-24 mg daily x 2-3 days). The adverse effects coincided with a rapid rise in activated T-cells after blinatumomab initiation, essentially confirming the hypothesis (22). Life-threatening neurologic adverse events were uncommon and generally reversible, but seizures have been observed in both the MRD and the active disease studies. Corticosteroids before the first dose and prior to dose escalation ameliorate some of the toxicities.

The adverse reactions in pediatric patients treated with blinatumomab were similar to those seen in adult patients with relapsed or refractory B-cell precursor ALL. Adverse reactions that were observed more frequently in the pediatric population compared to the adult population were pyrexia (80% vs. 61%), hypertension (26% vs. 8%), anemia (41% vs. 24%), infusion-related reaction (49% vs. 34%), thrombocytopenia (34% vs. 21%), leukopenia (24% vs. 11%), and weight gain (17% vs. 6%). In infants and children < 2 years of age, the incidence of neurologic toxicities was not significantly different than for the other age groups, but its manifestations were different (agitation, headache, insomnia, somnolence, and irritability). In the phase I/II open label blinatumomab study in pediatric patients with relapsed / refractory ALL, among the 70 pediatric patients treated on the trial, the most frequent grade 3 adverse events were anemia (36%), thrombocytopenia (21%), and hypokalemia (17%). Three patients (4%) and one patient (1%) had cytokine-release syndrome of grade 3 and 4, respectively. Two patients (3%) interrupted treatment after grade 2 seizures. Reports of compassionate use of blinatumomab in pediatric patients with relapsed / refractory ALL and prior ASCT have shown that blinatumomab did not induce nor exacerbate acute graft versus host disease (24, 25).

## 3.0 Drug Information

### 3.1 Blinatumomab

Each BLINCYTO (blinatumomab) package contains 1 vial BLINCYTO and 1 vial IV Solution Stabilizer.

BLINCYTO is supplied in a single-use vial as a sterile, preservative-free, white to off-white lyophilized powder for intravenous administration. Each single-use vial of BLINCYTO contains 35 mcg blinatumomab, citric acid monohydrate (3.35 mg), lysine hydrochloride (23.23 mg), polysorbate 80 (0.64 mg), trehalose dihydrate (95.5 mg), and sodium hydroxide to adjust pH to 7.0. After reconstitution with 3

mL of preservative-free Sterile Water for Injection, USP, the resulting concentration is 12.5 mcg/mL blinatumomab.

IV Solution Stabilizer is supplied in a single-use vial as a sterile, preservative-free, colorless to slightly yellow, clear solution. Each single-use vial of IV Solution Stabilizer contains citric acid monohydrate (52.5 mg), lysine hydrochloride (2283.8 mg), polysorbate 80 (10 mg), sodium hydroxide to adjust pH to 7.0, and water for injection.

Since blinatumomab will be administered via continuous intravenous route, it needs to be stabilized at low concentrations to prevent absorption to surfaces. Therefore, the IV bag must be conditioned by prior addition of a product-specific diluent (IV solution stabilizer), resulting in a final diluent concentration of 0.5 mM citrate, 25 mM lysine hydrochloride and 0.002% (w/v) polysorbate 80. Sterile water for injection and supplies required for reconstitution and injection of blinatumomab will not be provided to clinical sites.

